Pre-Analysis Plan:

Assessing the impact of the HIV prevention tool “Join-In-Circuit on AIDS, Love & Sexuality” in Zambia

[name] and [name]*

*Corresponding author: I received valuable feedback from [name], [name] and [name]. Please send correspondences to [name] at [contact].

Contents

1	Background	3
2	Design	4
2.1	Population	4
2.2	Randomization	6
3	Surveying	8
3.1	Baseline	8
3.2	Network mapping	9
3.3	Outcome measurement	10
3.4	Endline	10
4	Empirical Analysis	10
4.1	Overall effect	11
4.2	Targeting effect	12
4.3	Network estimands	12
4.4	Robustness	13
5	Final remarks	14
6	Supplementary Information	14
6.1	Blocking code	14
6.2	Survey instrument	15

11 Background

In Zambia, 13% of the 15 to 49 year old population lives with HIV. The highest number of new HIV infections is among young people (Central [Statistical Office \(CSO\) \[Zambia\]](#), [2015](#)). To counter the spread of the disease, developmental and governmental actors are increasingly relying on educational behavior change tools. A particularly widely used tool, implemented by the German Development Corporation (henceforth, GIZ), is the so-called “Join-In-Circuit on AIDS, Love Sexuality” (JIC). The JIC uses exercises, pictorial aids and edutainment strategies in an interactive circuit with six stations to teach kids about HIV. The tool aims to improve a) HIV and sexual reproductive health knowledge, b) HIV testing uptake, and c) demand for health services. Previous research ([name] [and Wong-Grunwald, 2017](#)) has investigated the direct effect of the JIC on knowledge about STIs as well as self-reported sexual behavior in Zimbabwe, and has found positive effects in both domains.

The present research project evaluates the JIC in Zambia. We randomly assign 170 participating schools to five different JIC treatment arms. The first two arms represent control schools. Here, no JIC will be implemented. The third arm implements the JIC among a random subset of students. The fourth arm implements the JIC among indegree central students. The fifth arm implements the JIC among edge betweenness central students. In each school, the JIC will be implemented in one pre-determined grade. Within each school at least 30 students will be selected. For larger schools, 20 per cent of students in the selected grade are selected.

The design allows us to tackle four distinct questions:

1. For each of the three targeting strategies, what is the overall effect of the JIC on all students?

2. For each of the three targeting strategies, what is the total effect of the JIC on participating students?

3. For each of the three targeting strategies, what is the spillover effect of JIC on non-participating students?
4. What is the most effective targeting strategy to maximize the above effects?

12 Design

2.1 Population

The study's population is the full universe of schools in the Choma and Livingstone provinces of Zambia (a total of 218 schools). The schools were provided to the authors by the Zambian Ministry of Education. 28 schools were randomly selected for a pre-test RCT (randomly assigning 14 schools to treatment, and 14 schools to control). For this reason, the final number of schools analyzed in this study is 204 (excluding already treated schools from the pilot RCT). The schools are split between primary (grade 1 to 7) and secondary schools (grade 8 to 12). In order to not interfere with exam periods, the Ministry of General Education and GIZ decided to implement the JIC among children in grade 6 in primary schools, and grade 11 in secondary schools. Before the intervention, we contacted all 204 eligible schools. During this process, several schools were found to not exist, to be double-counted or to be a different institution altogether (e.g., kindergartens mislabeled as primary schools). The final set of schools was then 170.

The descriptive statistics of the school sample is given in Table 1. On average, the schools have 80 students¹ and 74 percent of the sample are in Choma. 88 percent of schools are considered rural, i.e., they do not lie in a major town. 4 percent of the sample have received a JIC before. The school's funding is as follows. The vast majority (80 percent) are funded by the Government of the Republic of Zambia (GRZ).

¹We caution that the data behind this variable is highly noisy and based on estimates. For this reason, the data was not used when implementing our block-randomization scheme.

3 percent are funded by the community, 12 percent are privately funded and 5 percent are funded through non-standard grants. Schools' access to governmental and health facilities is captured by three variables. First is the distance to the nearest District Board of Education (DEBS, average of 36 kilometers). Second is the distance to the nearest so-called youth-friendly corner (YFC, average of 20km). Third is the distance to the nearest health facility (HF, average of 4km).

Table 1: Descriptive Statistics of Schools

		N	Mean	SD
School characteristics				
	Students	169	79.0	58.4
	Choma	170	73.5	44.2
	Primary	170	88.2	32.3
	Rural	170	60.0	49.1
	JIC before	170	3.5	18.5
Funding				
	GRZ	157	80.3	39.9
	Community	157	3.2	17.6
	Private	157	12.1	32.7
	Grant	157	4.5	20.7
Location				
	Lat	160	-16.8	2.8
	Lon	160	26.6	0.6
Facilities				
	Nearest DEBS (km)	169	36.4	34.8
	Lat nearest YFC	160	-17.1	0.5
	Lon nearest YFC	160	26.7	0.5
	Nearest YFC (km)	160	19.7	22.2
	Lat nearest HF	160	-17.0	0.6
	Lon nearest HF	160	26.7	0.5
	Nearest HF (km)	160	4.0	3.8

Notes: The Table shows the descriptive statistics of the school sample, showing the overall sample size (N), the average (Mean), and the standard deviation (SD) of the indicated variables.

2.2 Randomization

The 170 schools were randomly assigned to one of five treatment conditions.

1. Control 1 (No intervention) (34 schools)
2. Control 2 (No intervention) (34 schools)²
3. Treatment 1 (Random selection) (34 of schools)
4. Treatment 2 (Indegree centrality) (34 of schools)
5. Treatment 3 (Betweenness centrality) (34 of schools)

To leverage pre-treatment covariate data on the schools, we relied on an algorithmic block-randomization procedure proposed by Ryan Moore [\(2016\)](#). Specifically, we blocked on the province (Choma), the school type (Primary), urbanization (Rural) and whether a JIC was implemented before. All variables should, in theory, predict whether the JIC leads to positive outcomes pertaining to STIs. In particular, we would expect schools in Livingstone (an urban center), secondary schools, urbanized schools and those that have not seen a JIC implemented before to have the greatest potential to improve knowledge and self-reported behavior as a result of the JIC. The precise code for the blocking is attached to this application in the Supplementary Information. In Table 2, we report the resulting balance across treatment statuses. The table shows that our block randomization scheme produced very good balance across the treatment statuses for observable pre-treatment covariates.

²We included two random control groups so that one could be dropped in case a possible funding crunch. Indeed, during the baseline, some schools in Control 2 were dropped due to a funding shortage. While we were informed by the survey group that there was no precise selection criterion for dropping the schools, we will nonetheless exclude the schools in select robustness tests.

Table 2: Balance across treatment conditions

	Random		Indegree centrality		Betweenness centrality		Control 1		Control 2	
	Mean	SD	Mean	SD	Mean	SD	Mean	SD	Mean	SD
School characteristics										
Students	66	50	94	55	78	53	71	52	86	76
Choma	71	46	71	46	74	45	76	43	76	43
Primary	88	33	88	33	88	33	88	33	88	33
Rural	59	50	59	50	59	50	62	49	62	49
JIC before	3	17	3	17	3	17	3	17	6	24
Funding										
GRZ	78	42	82	39	80	41	77	42	83	38
Community	0	0	6	24	3	18	3	18	3	18
Private	16	37	12	33	17	38	13	34	3	18
Grant	6	25	0	0	0	0	6	25	10	30
Location										
Lat	-16	6	-17	1	-17	1	-17	0	-17	0
Lon	27	1	27	1	27	1	27	1	27	1
Facilities										
Nearest DEBS (km)	41	39	37	38	31	30	36	35	37	34
Lat nearest YFC	-17	0	-17	0	-17	0	-17	0	-17	0
Lon nearest YFC	27	1	27	1	27	0	27	0	27	0
Nearest YFC (km)	21	24	19	23	20	20	17	20	22	24
LAT nearest HF	-17	1	-17	1	-17	1	-17	0	-17	1
Lon nearest HF	27	1	27	0	27	0	27	0	27	0
Nearest HF (km)	4	4	4	4	4	4	4	4	3	3

Notes: The Table shows descriptive statistics of five different samples showing the average (Mean) and the standard deviation (SD) of the indicated variables.

13 Surveying

3.1 Baseline

The baseline data collection, conducted by a team of 10 trained enumerators divided into 3 groups, lasted about two months from March 16, 2017 to April 11, 2017 and from May 24, 2017 to July 11, 2017 for a total of 52 days. Data collection had to be interrupted during the month of April due to a month-long school break. The survey instrument is attached to this document. The prime reason for the baseline survey—in addition to collecting outcomes before the intervention takes place—was to map the entire friendship network in a given grade (more below).

Once data collection started, the survey team found additional ineligible schools that were either unreachable by car, did not have the targeted grades or were closed. Overall, the survey team managed to conduct a baseline in 98 out of the 102 schools in the treatment group (96% of the target), 28 out of 34 schools in the control 1 category, and 7 out of 34 in control 2. The final sample, thus, consists of 133 schools for the baseline survey. 37 of the schools are in Livingstone and 96 schools in Choma. 19 schools are secondary schools and 114 are primary schools. All students in either grade 6 (if primary school) or grade 11 (if lower secondary school) present on the day of baseline were interviewed for a total of 8,276 students.

Since some instruments are sensitive in nature (more below), we opted to administer self-administered surveys on tablet computers supported by ACASI (audio-assisted computerized assisted self-interview software) technology. Specifically, the survey was loaded unto the tablets and each question was accompanied by an audio file that read out loud the question in the desired language (options were Tonga and English). Students were given headphones for increased privacy. After hearing the question, students were to tap on the relevant answer. Finding the correct answer was facilitated by a) maximizing the number of questions with a vignette or picture or color coded, and by

b) positioning the answers on the left, middle, or right panel of the tablet and have the audio file explain where to find the answer. Two enumerators were present to help and assist in case of confusion or any other problem.

3.2 Network mapping

The network mapping was done as follows. First, enumerators collected attendance lists at every school for the assigned grade. Second, enumerators administered the survey, which included the following question: "Now, I want to know who are the friends that you spend time with in your grade. I am going to read you the names of all students in your grade. For every name, I want you tell me if the student is a friend of yours that you spend time with." Enumerators then recorded each friend of a given respondent on a separate list.

In a third step, the list was then passed on to the principal investigator (PI). In treatment group 1, a random subset of students was chosen for treatment. In treatment group 2, the PI used the R package *keyplayer* (An [and](#) Liu, [2016](#)), to identify the students with the highest in-degree centrality D_i , defined as the sum of incoming friendship nominations from the rest of the network. Specifically, $D_i = \sum_j w_{ji}$, where w_{ji} indicates friendship nominations from j to i . In treatment group 3, the PI used the same package to identify students with the highest edge betweenness centrality. It is defined as:

$$B^i = \sum_k g_{jk}^i, \text{ where } g_{jk}^i \text{ is the number of shortest paths between students } j \text{ and } k, \text{ and}$$

g_{jk}^i gives the amount of those paths running through student i . In other words, key-player selects the group of students who, combined as a pair, are directly connected to the highest number of different students compared to any other combination. The code underlying this procedure, including all realized assignments, is available upon request.

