4.2 Targeting effect

H2: We hypothesize that the overall effect of the JIC is strongest under edge-central targeting, intermediate under indegree targeting, and weakest under random targeting.

We estimate the contribution of targeting to the overall effect with the following equation:

$$Y_{ij} = \beta_0 + \beta_1' S_j + \beta_2 X_{ij} + \epsilon_{ij}$$

where S_j is a vector of indicator variables for random, indegree, and edge central targeted schools, and differences between the elements of β_1 evaluate the differences between targeting strategies.

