4.3 Network estimands

Guided by the same hypotheses as above, we also estimate total, spillover, and direct effects of the JIC on the same outcomes, and compare them across targeting strategies. We estimate the total effect of the JIC on targeted students separately for the three targeting strategies analogous to equation (1), except that we now restrict the samples to treated students in treated schools and comparable untreated students in control schools.⁴ We estimate the spillover effect of the JIC on non-targeted students separately for the three targeting strategies analogously to equation (1), except that we now restrict the samples

⁴Specifically, under random targeting, we compare randomly targeted students in treated schools to all students in untreated schools; under indegree targeting, we compare treated students in indegree-treated schools to the corresponding share of highest-indegree students in untreated schools; under edge-centrality targeting, we compare treated students in edge-centrality schools to the corresponding share of highest edge-centrality pairs in untreated schools.

to untreated students in treated schools and comparable untreated students in control schools. We estimate the direct effect of the JIC on targeted students under random targeting, except that we now restrict the sample to students in random-targeted schools, and estimate

$$Y_{ij} = \beta_0 + \beta_1 T_{ij} + \beta_2' X_{ij} + \epsilon_{ij},$$

where T_{ij} is an indicator equal to 1 if student i in random-targeted school j is treated and 0 otherwise.

The direct effect compares treated students in treatment schools to comparable un-treated students in treated schools. By comparing treated to untreated students in the same school, this effect removes the indirect effect via peers. Note: in our study, however, the direct effect can only be estimated with random targeting, because only with random targeting are treated and untreated students in a given school comparable to each other.

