6.1 Blocking code

```
rm(list = ls())
setwd("")

data <- read.csv("population_cleaned.csv")
data$id <- seq(1:length(data[,1]))
set.seed(52273)
library(blockTools)

data$groups = 1
data$nearest_yfc <- ifelse(is.na(data$geolat$yfc), 1, 0)

out <- block(data,
              groups = "groups",
              n.tr = 5,
              id.vars = c("id"),
              block.vars = c("choma_vs_livingston", "primary_vs_secondary", "rural_vs_urban", "jic_implemented_before"), #we only block on non
              #dist_debs_km", "dist_yfc_km", "dist_hf_km"),
              #grz", "community", "private", "grant", "geo_lat", "geolat",
              #male_pupil", "female_pupil", "pre_test"),
              algorithm = "optGreedy",
              distance = "mahalanobis",
              level.two=FALSE,
              verbose=TRUE)

assg <- assignment(out, seed = 5212)
outCSV(out)
```

```

treatments<- read.csv("Group1.csv")
treatment1<- cbind(treatments[2], "random")
colnames(treatment1)<- c("Unit", "Treatment")
treatment2<- cbind(treatments[3], "change-maker")
colnames(treatment2)<- c("Unit", "Treatment")
treatment3<- cbind(treatments[4], "change-maker-friends")
colnames(treatment3)<- c("Unit", "Treatment")
treatment4<- cbind(treatments[5], "control1")
colnames(treatment4)<- c("Unit", "Treatment")
treatment5<- cbind(treatments[6], "control2")
colnames(treatment5)<- c("Unit", "Treatment")
treatment<- rbind(treatment1, treatment2, treatment3, treatment4, treatment5)
treatment <- treatment[order(treatment$Unit),]
treatment <- as.matrix(treatment[2])
data<- data[order (data$id),]
data$treatment <- treatment
table(data$treatment)

data$treatment~change-maker<-c(ifelse(data$treatment=="change-maker",1,0))
data$treatment~change-maker-friends<-c(ifelse(data$treatment=="change-maker-friends",1,0))
data$treatment~random<-c(ifelse(data$treatment=="random",1,0))
data$treatment~control1 <-c(ifelse(data$treatment=="control1",1,0))
data$treatment~control2 <-c(ifelse(data$treatment=="control2",1,0))

#write.csv(data, "randomization.csv")

```

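### Treatment 3 selection is described by three rules that do not agree, and footnote 4 builds the total-effect control comparators on an undefined pair version of it

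*SAP*

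**What the plan says.** Section 3.2 describes the selection three times in succession:

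- The named measure: "the PI used the same package to identify students with the highest edge betweenness centrality".
- The definition, a score indexed by student i, in which one term "gives the amount of those paths running through student i".
- A restatement offered as equivalent: "key-player selects the group of students who, combined as a pair, are directly connected to the highest number of different students".

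Other sections use further variants. Section 1 says "The fifth arm implements the JIC among edge betweenness central students". The arm list in section 2.2 has betweenness centrality without the word edge. H2 in section 4.2 predicts that "the overall effect of the JIC is strongest under edge-central targeting".

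Footnote 4 in section 4.3 sets the control comparators for the Treatment 3 total effect as "the corresponding share of highest edge-centrality pairs in untreated schools". For the spillover effect, section 4.3 asks only that the untreated control students be comparable. Section 3.2 adds that the selection code and the realized assignments can be had on request.

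**The concern.** The three descriptions in section 3.2 rank different things. Edge betweenness scores a tie between two students. Paths running through a student give the betweenness of that student. Direct connection to the most different students is coverage by immediate contacts, and shortest paths play no part in it. The plan presents them as one rule and does not say which governs.

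Two things are at stake. First, H2 ranks this arm strongest and the fourth research question asks which targeting strategy is best, so a reader must know what the strategy was. Second, the treated students have been chosen by code, but their counterparts in control schools are chosen at the analysis stage. If footnote 4 is applied literally and the code used something else, the two groups differ by selection as well as by treatment.

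**Working it through.** The plan gives no figure to reproduce, so the check compares the wording, tests whether the rules can pick different students, and traces where the rule enters the analysis. The displayed formula in section 3.2 is not relied on; the words around it are enough.

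**1. The wording side by side**

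| Place | What is ranked | By what |
|---|---|---|
| Section 3.2, named measure; section 1; H2 | Students, by a score that belongs to ties | Edge betweenness |
| Section 3.2, definition | A student | Shortest paths through the student |
| Section 3.2, restatement | A pair or group | Number of distinct direct contacts |
| Section 2.2 | Not stated | Betweenness |
| Footnote 4 | A pair | Edge centrality, with no score given |

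**2. Can the rules pick different students?**

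Take an illustrative network (an assumption, not from the plan): two hubs with five leaves each, joined by a bridge of two students. That is 2 + 10 + 2 = 14 students. Any two students are joined by exactly one path, so the scores can be counted by hand.

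- *Hub, student betweenness.* Removing a hub leaves five single leaves and a group of 14 − 1 − 5 = 8. Pairs separated: 5 × 4 / 2 + 5 × 8 = 10 + 40 = 50, or 100 counting both directions.
- *Bridge student, student betweenness.* Removal leaves groups of 6 and 7. Pairs separated: 6 × 7 = 42, or 84 in both directions.
- *Ties, per direction.* Bridge tie: 7 × 7 = 49. Hub-to-bridge tie: 6 × 8 = 48.
- *Direct contacts.* Each hub has 5 + 1 = 6, so the two hubs together reach 12 others. The bridge pair reaches 2 others.

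With two places, student betweenness and coverage both take the hubs, and edge betweenness takes the bridge pair.

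With four places, student betweenness takes the hubs and then the bridge students. Edge betweenness, reading students off the ties in order (49, then 48), reaches the same four. Coverage fills two places and then stops discriminating, because the hubs already reach all 14 − 2 = 12 others; the last two places are ties.

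No two of the three rules therefore agree throughout.

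**3. The step from pairs to students**

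Section 1 requires at least 30 students per school, or 20 per cent of the grade in larger schools; 20 per cent exceeds 30 only above 30 / 0.20 = 150 students. The baseline average in section 3.1 is 8,276 / 133 = 62 students per school, so a typical list holds 30 of about 62. Thirty places could be 15 separate pairs (30 / 2), or more pairs if a student may appear in several. The plan does not say which, nor how ties are broken.

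**4. Where the rule enters the analysis**

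- *Overall effect and H2 (sections 4.1 and 4.2).* All students are compared by school-level arm indicators. The selection rule enters no term.
- *Total effect, Treatment 3.* The rule determines who the control comparators are. It enters directly, through footnote 4.
- *Spillover effect, Treatment 3.* Comparators are naturally the control students whom the rule would not have selected, but the plan does not say so.
- *Direct effect.* It is estimated under random targeting only, so it is unaffected.

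**The case against.** The best reply is that the texts do not carry equal weight. The student-indexed score is introduced as the definition and section 2.2 agrees with it, so the word edge may be misapplied and the pair sentence a poor paraphrase. The selection is already made, and the code and assignments are available. That is a plausible reading, but the plan does not state it, and footnote 4 uses the edge and pair wording in an analysis step. Access to the code shows which students were treated; it does not fix how control comparators will be chosen.

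Four stronger readings are tempting and are not supported:

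- *The H2 result is invalid or at risk numerically.* It is not. The contrast is by randomized arm over all students, and no wording changes it. Only the name and meaning of the arm are in doubt.
- *The control comparators are in fact picked by a different rule.* The plan does not say that. Footnote 4 uses the edge-centrality term for treated and control students alike and asks for the corresponding share. The harm is conditional on how the footnote is carried out.
- *The label "change-maker-friends" in the section 6.1 code is a further definition.* That code assigns schools and selects no student; Treatment 2 has an equally informal label there.
- *Footnote 4 also governs spillover.* It is attached to the total-effect sentence only.

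Nor can a percentage overlap between the selected lists be offered. It would depend on assumed friendship networks and on tie-breaking and edge-to-student rules that the plan does not give.

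**Conclusion.** The point holds as a contradiction in a stated rule with one analytic consequence. Section 3.2 gives three non-equivalent descriptions of the Treatment 3 selection, and footnote 4 carries an undefined pair version into the choice of control comparators for the total effect. The H2 overall-effect contrast stands as a comparison of arms, with the strategy behind it unclear. The Treatment 3 total-effect contrast is like for like only if the control comparators come from the same rule that selected the treated students, and the plan does not secure that.

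The example network is an assumption and shows only that the rules can select different students, not how often they would in these schools. The size of any bias is unknown.

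**What to change.** - Read the metric and the selection algorithm actually used from the saved keyplayer code. State that single definition in section 3.2, including any pair score, the step from pairs to the required number of students, and the handling of ties. Delete the other descriptions.
- Use one name for the arm in sections 1 and 2.2, in H2 and in footnote 4.
- In footnote 4, replace the edge-centrality pairs with the students selected by running the same code on the control-school baseline networks.
- State in section 4.3 that the remaining, non-selected control students are the comparators for the Treatment 3 spillover contrast.

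The cost is SAP wording and one run of existing code on the control schools with a baseline survey (28 + 7 = 35 in section 3.1). No treatment, assignment or data collection changes. The revision should be made before endline outcomes are examined, so that the comparator rule is not chosen with results in view.
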